## **4. OBJECTIVES**

- Assess baseline fatigue and anxiety levels prior to HRM.
- Evaluate the effect of the HRM program on fatigue and anxiety post-intervention.
- Compare post-intervention changes between the intervention and control groups.
- Examine associations between socio-demographic/clinical characteristics and HRM effectiveness.

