## 6. METHODOLOGY

- **Study Design:** Two-group parallel Randomized Controlled Trial (RCT) with a 1:1 allocation ratio.
- **Setting:** Hemodialysis units in Iraq.
- **Sample Size:** 70 adult patients receiving MHD (35 in the intervention group, 35 in the control group).
- **Intervention Group:** Received eight 21-minute HRM sessions over four weeks (two sessions per week) during routine hemodialysis, in addition to usual care.
- **Control Group:** Received usual care only (routine dialysis nursing care) without HRM.
- **Data Collection Time Points:**
  - T0: Baseline (before the first session).
  - T1: Mid-intervention (after the 4th session).
  - T2: Post-intervention (after the 8th session).

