## 7. STUDY INSTRUMENTS

1. Demographic and Clinical Characteristics Questionnaire (age, gender, education, income, duration of HD, etc.).
2. Arabic FACIT-Fatigue Scale (Version 4).
3. Arabic Beck Anxiety Inventory (Ar-BAI).

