## **9. STATISTICAL ANALYSIS PLAN**

- Normality Testing: Shapiro-Wilk test will be used to assess the normal distribution of continuous variables.
- Within-Group Comparisons: Parametric tests (e.g., Repeated Measures ANOVA) for normally distributed data, and non-parametric tests (e.g., Friedman test) for non-normal data across the three time points (T0, T1, T2).
- Between-Group Comparisons: Independent t-test or Mann-Whitney U test to compare post-intervention scores between the intervention and control groups.
- Multiple Comparisons: Bonferroni correction will be applied for post-hoc pairwise comparisons to control Type I error.
- Associations: Chi-square or Fisher's exact tests will be used to examine relationships between demographic/clinical characteristics and HRM effectiveness.
- Clinical Significance: Minimal Clinically Important Difference (MCID) will be calculated to determine the practical relevance of fatigue and anxiety score improvements. Analysis will be performed using SPSS.

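### Chi-square or Fisher tests of patient characteristics against an undefined HRM effectiveness cannot separate characteristics that predict outcome from those that modify the HRM effect

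*Combined protocol and SAP*

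**What the plan says.** The last of the four objectives in Section 4 is to "Examine associations between socio-demographic/clinical characteristics and HRM effectiveness". Section 9 gives it one method: chi-square or Fisher's "exact tests will be used to examine relationships between demographic/clinical characteristics and HRM effectiveness".

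The characteristics come from the questionnaire in Section 7 ("age, gender, education, income, duration of HD, etc"). Five are named and the list is open-ended.

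The plan does not define effectiveness for this purpose. It gives no responder rule, cut-off or time point, and does not say whether one arm or both enter the table. The nearest text is the clinical-significance item in Section 9: "Minimal Clinically Important Difference (MCID) will be calculated to determine the practical relevance of fatigue and anxiety score improvements". It states no value and is not linked to the association tests.

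The only between-arm analysis in Section 9 is overall, not by characteristic: "Independent t-test or Mann-Whitney U test to compare post-intervention scores between the intervention and control groups". No interaction, no subgroup treatment effect, and no model containing both arm and characteristic appears anywhere.

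**The concern.** Sections 2 and 3 frame the effect of HRM as a difference from usual care. No single patient shows that difference, because each is observed under one condition only. A contingency table nevertheless needs one category per patient, so the category has to be built from that patient's own outcome: change from baseline, reaching an MCID, or a severity class at T2.

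A table of characteristic by outcome category shows who did better. It does not show who did better because of HRM. Patients with a given characteristic may improve more, or end with better scores, under usual care as well. The randomised control arm could reveal this, but the planned test does not use it as a comparator.

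At stake is the answer to the last objective. A prognostic characteristic could be reported as identifying patients who benefit from HRM, and a real modifier could be missed if prognosis runs the other way.

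**Working it through.** **Inputs from the documents.** 35 patients per arm and 1:1 allocation (Section 6); five named characteristics (Section 7); two outcomes, fatigue and anxiety; chi-square or Fisher tests (Section 9). The plan states no figure for this analysis to reproduce. It gives 70 as the sample size without alpha, power, effect size or SD.

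**Assumed inputs.** Two-sided 5% level; a binary characteristic with 50% prevalence; normal scores with SD 1. None of these is in the documents.

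**Step 1: error rate in the HRM arm, by formula.** Let the characteristic shift change by g SD equally in both arms, so that it does not modify the HRM effect. Call a patient a responder if change lies above the mid-point between the two subgroups. The response rates are then Φ(g/2) and Φ(−g/2), with 35/2 = 17.5 patients per subgroup. The null standard error is √(2 × 0.25/17.5) = 0.169, so the critical difference is 1.96 × 0.169 = 0.331.

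- g = 0.5: rates 0.599 and 0.401, difference 0.197, standard error 0.166. Rejection = Φ((0.197 − 0.331)/0.166) = Φ(−0.81) = 21%.
- g = 0.8: rates 0.655 and 0.345, difference 0.311, standard error 0.161. Rejection = Φ((0.311 − 0.331)/0.161) = Φ(−0.13) = 45%.

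Simulation of the same setting (2,500 trials each) gives 20% and 45%. The two-arm interaction test rejects in 4–5%.

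**Step 2: other readings of the table.** In a second simulation (5,000 trials per row), a responder improves by at least 0.5 SD and the T0–T2 correlation is 0.5. Fisher's test replaces chi-square when an expected count is below 5. The interaction comes from a baseline-adjusted linear model. The HRM effect is a constant 0.6 SD unless stated.

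| Scenario | Table, HRM arm | Table, arms pooled | Interaction |
|---|---|---|---|
| Characteristic unrelated to change or baseline | 4.8% | 5.3% | 4.8% |
| Prognostic only, 0.5 SD | 18% | 33% | 4.8% |
| Prognostic only, 1.0 SD | 51% | 87% | 4.6% |
| Prognostic 0.8 SD, HRM has no effect | 42% | 73% | 5.1% |
| Baseline gap of 1 SD | 18% | 34% | 4.4% |
| Real modification (0.2 v 1.0 SD), opposing prognosis −0.8 SD | 4.4% | 15% | 46% |

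In the first five rows no subgroup benefits more, so every rejection is false as a statement about HRM benefit. In the last row the modification is real, and the HRM-arm table misses it. Pooling the arms does not help, because the table still has no arm term.

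**Step 3: power of the interaction test at this sample size.** With 17.5 patients in each of four cells and no covariate adjustment, the standard error is √(4/17.5) = 0.478 SD.

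- 0.5 SD: Φ(0.5/0.478 − 1.96) = Φ(−0.91) = 18%.
- 0.67 SD: Φ(0.67/0.478 − 1.96) = Φ(−0.56) = 29%.
- 1.0 SD: Φ(1.0/0.478 − 1.96) = Φ(0.13) = 55%.
- 80% power needs (1.96 + 0.84) × 0.478 = 1.34 SD. The overall comparison needs (1.96 + 0.84) × √(2/35) = 0.67 SD.

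**The case against.** **Severity.** This is the last of four objectives. The research question, the hypothesis and the overall between-arm comparison do not depend on it. That stands, and it rules out treating the point as a threat to the main result.

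**What the table contains.** A reader might infer that the plan classifies HRM-arm patients by change from baseline. The documents do not say so. Effectiveness is undefined and the arm or arms are not stated, so 35 HRM patients is an assumption in the figures above. The argument needs less: any per-patient category has the same limitation.

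**Certainty of a wrong answer.** A reader might infer that prognostic characteristics are bound to be reported as predictors of benefit. The figures do not support that. At 0.5 SD about 80% of trials would not declare the characteristic, at 0.8 SD about 55% would not, and an unrelated characteristic is declared at about the nominal rate. The documents give no prognostic effect sizes.

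**Regression to the mean.** Splitting patients by baseline score would give larger error rates for a change-based category. Section 7 does not name baseline score as a characteristic, however. For the named ones the mechanism matters only if they are related to baseline, as in the assumed 1 SD gap above.

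**Power and categories.** Low power of the chi-square test is not a reason to switch, since the interaction test is also weak at this size. Nor does the test alone force the anxiety score into classes: Section 5 already defines four. The case rests on which question each test answers.

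**Conclusion.** The concern holds for the fourth objective. The planned tables can show which characteristics go with a better patient-level outcome. They cannot show which characteristics modify the effect of HRM.

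Under the stated assumptions, a purely prognostic characteristic of 0.5 or 0.8 SD is declared associated in about 20% or 45% of trials, against about 5% for the interaction test. These rates depend on the assumed strength of prognosis, the 50/50 split, the responder rule and use of the HRM arm alone. The structural limitation does not depend on any of them.

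It should be fixed, as a matter of a supporting objective. The missing definition of effectiveness is a gap on the face of the text.

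**What to change.** For each outcome, fit a linear model of the T2 score in all 70 patients with baseline score, arm, characteristic and the arm-by-characteristic interaction. Name a short list of characteristics in advance and keep age and duration of HD continuous. Report each interaction estimate with its 95% CI and label the results exploratory.

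If the chi-square or Fisher tests are kept, define the outcome category (measure, cut-off, time point and arms used) and describe the results as predictors of outcome, not of benefit from HRM.

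**Cost.** No new data are needed, but the model is new: Section 9 has no baseline-adjusted model to extend. It takes one model per characteristic and outcome, so 5 × 2 = 10 if all five named characteristics are kept. The main downside is the low power shown above, about 18% for a 0.5 SD interaction and 55% for 1.0 SD. Most results will be inconclusive, and the report should say so.
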